### Visit 1 (Day 0):

- 1) Consenting and confirmation of inclusion & exclusion criteria
- 2) General History and Physical Exam (including review of concomitant medications)
- 3) Urine Pregnancy test for woman of childbearing potential. Counseling on acceptable birth control measures to use throughout treatment period (28 days) and until 30 days after stopping study drug
- 4) Questionnaire to clinically characterize AD
- 5) Clinical score for atopic dermatitis
- 6) Identification of the target area to be treated with NANODOX® and skin biopsy locations. Arms will be the preferable areas if lesions are present, otherwise trunk or lower extremity
- 7) Digital pictures of the target area and area used for biopsy
- 8) Non-invasive skin barrier Measurements: TransEpidermal Water Loss (TEWL). Optional: pH and Stratum Corneum (SC) hydration measurements may also be performed
- 9) Repeated tape strippings (0, 5, 10, 15 tape-strippings with Cuderm™ tape) of non-lesional and lesional locations from treated area will be collected as part of the TEWL assessment and to assess for SC cohesion/integrity (rate of change in TEWL with repeated strippings).

Serial measurements of TEWL will be performed after tape stripping as previously describedxiii. This will also allow collecting proteins (eluded from the tape) for proteases activity assessment.

- 10) Skin swab
- 11) Optional Skin biopsy (5 mm punch) of a representative skin in the same anatomical area or symmetrical, avoiding the area that will be treated. This biopsy may be performed on D28 at the same time as the post treatment biopsy.
- 12) Venous blood draw to monitor AD biomarkers
- 13) Dispense NANODOX® for two following weeks (14 +/- 2 monodose packages)
  - Subjects will be instructed to keep the NANODOX refrigerated at + 4C; subjects will be provided a cooler and ice packs keep the products refrigerated during transport.
- 13) Provide instructions to complete at home diary.
- 14) Provide date of Visit 2 and “morning of appointment” instructions

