- **Tape stripping for proteases activity measurements:** the most superficial layers of the skin will be collected by tape stripping using D-squame (D-squame $\text{\textcircled{R}}$ , CuDerm, Dallas TX, USA – **Figure 2**). This is a well-established method used in clinical research to gently perturb the skin barrier. The first tape will be discarded to eliminate dirt and remnants of skin products. Each tape will be gently pressed against the skin with standardized pressure for 10 seconds (sec) using a standardized pressurizer (D500–D-squame $\text{\textcircled{R}}$  pressure instrument, CuDerm, Dallas, TX, USA – **Figure 2**). Non-lesional skin samples will be collected from the volar side of the forearm and lesional skin samples will be collected from an easily accessible area, such as arms or lower legs.

All subjects will have 20 consecutive tapes collected from lesional skin and 20 consecutive tapes from non-lesional skin. Once the tapes have been collected, as part of this study, we will test different methods to elute the skin proteins from the tapes.

The corneocytes (cells in the most superficial layer of the skin) or their cellular contents that adhere to the discs must be released from the adhesive coating for subsequent analytical steps. So far several groups were able to use this non-invasive method to analyze for the presence of biomolecules, drugs and other cellular constituents.

- **Skin barrier measurements:** Transepidermal water loss/TEWL, +/- pH and SC hydration measurements will be obtained on treatment area at a non-lesional site and on a site of inflammation. For each of the specific measurements, a probe will be gently applied on the skin surface for few (up to 30) seconds. We will perform all measurements in a climate-controlled examination room with temperatures ranging 20-22 $^{\circ}$ C and consistent humidity (preferably 40%). The patient must be very comfortable in

the room in which they are being tested to ensure that perspiration due to stress or acclimatization does not alter the TEWL. TEWL will be measured at baseline and after tapestripping. SC hydration and surface pH will be assessed on non-lesional and lesional skin using the Corneometer® CM825 and Skin-pH-Meter® PH 905, respectively (Courage and Khazaka Electronic GmbH, Kohn GE – **Figure 1**). TEWL will be assessed using the AquaFlux (Biox, London UK). These measurements should provide data to determine if the treatment has an effect on skin barrier integrity.

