### **Secondary Outcomes:**

1. Improvements of itch score (0-5 scale) in lesional skin, before and after treatment at each time point. 2. Will evaluate Staphylococcal Aureus rate of colonization (positive or negative), difference in number of growth (0 to 3+++ ) and antibiotic sensitivity pre and post treatment. Doxycycline could have an effect on AD lesions just by reducing the Staphylococcal Aureus colonization. By integrating these findings with clinical outcomes, drug penetration and molecular changes we will be able to start to address this question. 3. Improvement of barrier function in non-lesional (normal appearing) and lesional skin pre and post treatment (V1 to V3). We will expect that clinical improvement parallels with improvement of barrier function, such as reduced TEWL, increased stratum corneum hydration and reduced pH in active treatment areas. On the other hand, worsening of the measurement will suggest damaging effect of the treatment on the skin, which could be indication of subclinical irritation induced by the treatment and/or vehicle.

The purpose of this study is a proof of concept. We are adopting a similar strategy to Phase II cancer trials that seek a clinically significant response. Using exact binomial methods, we shall obtain point and interval estimates for the fraction of subjects who respond as (a) At least EASI 50% by visit 2 or 4 and (b) At least EASI 75% by visit 2 or 4. We shall also tabulate the IGA score from baseline to visit 4. We would consider 6 or more responses (a) in 15 subjects as promising. The probability of declaring a promising result when the true response rate is 60% or higher is over 96% (power).

Side effects and baseline characteristics will be tabulated qualitatively. The blinded pre-vs post evaluation will be analyzed for IGA scores by the Wilcoxon sign-rank test.

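### The tape-stripping method names sites outside the treated area, so tape protease and strip-based integrity data can come from skin that never received the gel

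*Combined protocol and SAP*

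**What the plan says.** Section 3 of the combined protocol and SAP describes tape stripping in two places, and they name different skin.

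- **Visit 1 (Day 0), item 9** asks for repeated strippings "of non-lesional and lesional locations from treated area will be collected as part of the TEWL assessment and to assess for SC cohesion/integrity". It gives the same tapes a second use: "This will also allow collecting proteins (eluded from the tape) for proteases activity assessment".
- **Study procedures & methods, tape-stripping bullet:** "Non-lesional skin samples will be collected from the volar side of the forearm". For diseased skin, the bullet leaves the choice of site open: "lesional skin samples will be collected from an easily accessible area, such as arms or lower legs". It does not mention the treated area.
- **Visits 2, 3 and 4** repeat the stripping series without naming a site.
- **Target area.** Visit 1, item 6: "Arms will be the preferable areas if lesions are present, otherwise trunk or lower extremity". Under Study Design, the gel goes on the target lesion and the normal-looking skin next to it, a patch about the size of an index card.
- **Tape count.** The visits list a series of 0, 5, 10 and 15. The method bullet says "All subjects will have 20 consecutive tapes collected from lesional skin and 20 consecutive tapes from non-lesional skin", with the first tape thrown away.
- **Outcome concerned.** Secondary outcome 3 in section 5: "Improvement of barrier function in non-lesional (normal appearing) and lesional skin pre and post treatment (V1 to V3").

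**The concern.** The trial's hypothesis is that the gel blocks protease activity in the skin and so restores the barrier. A before/after change can test this only on skin that was dosed. If staff follow the method bullet, the non-lesional tapes come from a forearm that is undosed unless the patch happens to cover it, and the lesional tapes may come from a lesion other than the target.

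Two features make this more than a loss of signal.

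- **Other drugs.** Section 3 stops topical treatments only in the selected area, and subjects may keep using them elsewhere at a stable dose. The optional screening visit applies the washout to the treatment and biopsy sites, not to a stripping site elsewhere. Tapes from another lesion may therefore reflect a steroid or calcineurin inhibitor.
- **Site mixed with time.** Staff could follow the Visit 1 text at baseline and the method bullet at Visits 2 to 4, which name no site. The change from baseline would then also be a change of anatomical site.

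The tapes matter because they are the only protease measure that is not optional. Biopsies are optional, and the comparison biopsy avoids the treated area and may be taken on Day 28. Only the tapes can give a before/after protease comparison at the treated site.

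**Working it through.** **1. The plan's own figure.** The only design calculation is the power for 6 or more EASI50 responses in 15 subjects at a true rate of 60%. The exact binomial gives P(X ≥ 6 | n = 15, p = 0.60) = 0.9662, which agrees with the stated value of over 96%. It uses no tape data, so this point does not touch it.

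**2. The site texts side by side.**

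| Text | Non-lesional tapes | Lesional tapes |
|---|---|---|
| Visit 1, item 9 | inside treated area | inside treated area |
| Visits 2 to 4 | not stated | not stated |
| Method bullet, tape stripping | volar forearm | any accessible site; arms or lower legs as examples |
| Method bullet, skin barrier | treatment area (TEWL, pH, hydration) | treatment area (TEWL, pH, hydration) |

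**3. When the two stripping rules coincide.** Both conditions must hold: the patch includes volar forearm skin, and the stripped lesion is the target lesion. The plan requires neither. With a target on the trunk or lower extremity, the first condition fails for certain. With an arm target, it may or may not hold.

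**4. Conflict within Study procedures & methods.** The skin barrier bullet puts TEWL on the treatment area and has it read again after stripping. The tape-stripping bullet strips elsewhere. Both cannot be followed when the stripped site lies outside the patch.

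**5. Which measures are exposed.**
- Tape protease activity: directly.
- Rate of TEWL change with stripping: yes, because the slope belongs to whichever site was stripped.
- TEWL before stripping, pH and hydration: no, because they are placed on the treatment area.
- EASI50 rule: no.

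**6. Tape count.** If the discarded tape is one of the 20, then 20 − 1 = 19 remain for assay. If it is extra, 20 + 1 = 21 are applied. The same question applies to the series ending at 15. Integrity is defined as TEWL change against strip number, so the numbering has to be fixed.

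**7. Size.** Let s be the share of subjects sampled off the patch, d the true change on treated skin and e the change off it. The expected mean change is (1 − s)d + s·e. The documents give none of s, d or e. At s = 0 the result is d, and at s = 1 it is e. Because other topicals may be in use off the patch, e cannot be taken as zero.

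**The case against.** The strongest reply is that this is a wording slip with narrow reach. Much of that stands.

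- **Barrier outcome and irritation.** A reader might infer that secondary outcome 3 as a whole, and the check for subclinical irritation on normal-looking skin, would be measured on undosed skin. The documents do not support this. The skin barrier bullet keeps TEWL, pH and hydration on the treatment area. Section 5 ties subclinical irritation to worsening of those readings, and visible irritation is noted at every visit.
- **Status of the protease data.** Tape protease activity is not a listed primary or secondary outcome, and the method bullet presents it partly as a trial of elution methods. Biopsies also measure proteases. This lowers the stakes, but the biopsies cannot supply a before/after comparison at the treated site.
- **Lesional wording.** Arms or lower legs overlaps with the target-area rule, so the text can be read as describing the target lesion. That is fair: the lesional half is loose rather than flatly contradictory. The clear conflict is the forearm.
- **Visit schedule.** It would be too much to say that the schedule as a whole fixes stripping in the treated area. Only Visit 1 does.
- **Tape count.** A run of 20 tapes with TEWL read after 0, 5, 10 and 15 would fit both texts. The plan does not say this is meant.
- **Numerical loss.** A reader might assume half the subjects are sampled off the patch and conclude that four times as many are needed for the same power, since 1/(1 − 0.5)² = 4. That needs s = 0.5, no change off the patch and constant variance. None of these is in the documents, and no sample size is tied to tape data. Totals of tapes per subject would also need assumptions about sites and visits that the plan does not state.

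None of this removes the conflict over where to strip.

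**Conclusion.** The concern holds within limits. The current text gives two incompatible stripping rules for non-lesional skin and a loose one for lesional skin, and nothing at Visits 2 to 4 settles which applies. Following the method bullet can put protease samples and the strip-based integrity slope on skin that was never dosed and may be under other topical treatment.

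The reach is the exploratory tape protease readout and one component of one secondary outcome. The conclusion rests on the text alone, plus the fact that the plan allows targets on the trunk or lower extremity. How many subjects would be affected, and by how much the change would be distorted, cannot be derived from the documents. The point should be corrected because those tapes carry the mechanistic hypothesis. It does not threaten the trial's decision rule.

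**What to change.** - **Site.** In the tape-stripping bullet and at each of Visits 1 to 4, state that lesional and non-lesional tapes both come from recorded locations inside the treated area. Adjacent spots at successive visits are acceptable. Identical spots should not be required: Visit 1 does not ask for them, the plan itself says stripping perturbs the barrier, and re-stripping the same skin could disturb later readings.
- **Count.** Reconcile the series ending at 15 with the 20 consecutive tapes. Give one count, the strip numbers at which TEWL is read, and whether the discarded first tape is included. The documents give no protein-yield requirement, so the choice of count is the sponsor's.
- **Forearm.** If a forearm sample is still wanted, label it an untreated reference and do not pool it with treated-site data.

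The cost is a wording change with no added procedure. One practical check is needed: two sites at four visits is 2 × 4 = 8 strippings, and the sponsor should confirm that separate spots fit within the patch. The change should be made before enrolment if possible, because baseline tapes taken at the wrong site cannot be collected again once dosing starts.

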#### **4. RISK, BENEFITS and PROTECTION AGAINST RISKS**

##### **Risks Associated with Digital Picture**

There are no known risks for the digital picture. The image will not include identifying features and will be labeled with study subject ID and date. Pictures will be taken with a dedicated camera, stored on a secure server and transferred into RedCap database.

##### **Risks Associated with Barrier Assessments**

There are no known risks for the barrier assessments.

##### **Risks Associated with Tape Stripping**

The risks associated with tape stripping, theoretically, include the rare possibility of an allergic reaction to the tape and infection. Since the tape is removed immediately after application, the risk of reaction is extremely low. We will exclude study subjects with known allergy to tapes or adhesive material. In previous and ongoing studies involving tape stripping, it has been noted that a very mild erythema may develop immediately after a series of tape strippings on one localized area of skin, presumably due to the mild mechanical disturbance. The erythema is expected to resolve within 12 hours without sequelae. The risk of skin infection is extremely low since only superficial skin layers are removed. Subjects will be provided with wound care information and a department phone number to contact should they have any concerns.

##### **Risks of Phlebotomy**

The risks of having blood drawn include some pain when the needle goes in, and a small risk of bruising and/or infection at that site. Some people will get lightheaded, nauseous, or faint. 4mLs is approximately 1 teaspoon of blood and is not likely to cause lightheadedness, however subjects will be observed after blood draw to be sure they are comfortable with deambulation.

Subjects will be encouraged to drink plenty of water prior to the blood draw. Phlebotomy will be performed at the antecubital fossa to minimize pain and bruising. Subjects will be seated during

the blood draw to minimize dizziness and any risk of falling. Pressure will be applied to the site after the draw and a band-aid will be applied to minimize the risk of bleeding and infection.

### **Risks of Punch Biopsy**

The biopsies will be no larger than 5 mm in diameter (about a pencil eraser head). A nonabsorbable suture (1-2 stiches) will be placed in each site for hemostasis and enhanced wound healing. A small scar will remain at the site. The scar will be smaller than the initial biopsy but may also be hypo- or hyperpigmented. Sutures will be removed in 14 (+/- 2) days. The risks of this procedure include adverse reaction to anesthesia (lidocaine), pain, bleeding, infection and hypertrophic scars or keloids. Patients with a history of Novocain or lidocaine allergy or a history of keloid formation will not be allowed to participate in order to minimize the risk of adverse reactions. Biopsy will be performed after injecting a local anesthetic to minimize pain. A pressure bandage will be applied to the biopsy site to minimize the risk of bleeding and infection. Written wound care instruction will be provided to the subjects after the procedure. In case of increased redness, pain or oozing of the sites subjects will be instructed to call the dermatology department if appropriate subjects will be asked to come to clinic in the next 24-48 hours for wound check.

### **Risks of NANODOXY® 1% hydrogel**

Subjects may experience local irritation including redness, pain, stinging or burning sensation in the treatment area. Systemic doxycycline can enhance sensibility to the sun light. It is possible that topical application might temporarily enhance risk of sunburn in the treated site. To minimize risk of sunburn we will instruct the subjects to apply the topical at bedtime and rinse off in the morning. In case of sun exposure subjects should use appropriate sun protection (SPF >30 or clothing). Some patients may experience some irritation from the NANODOXY® hydrogel especially in areas of open skin from scratching. Some patients may experience increased dryness from the hydrogel formulation. All patients will be advised to moisturize in the morning and use gentle body wash to minimize these potential side effect.

As for any antibiotic, there might be a risk of inducing antibiotic resistance. To minimize the risk the drug will be used only until the lesion is active/visible. Also we will be monitoring for bacteria growth during the study to determine possible change in bacteria contamination as well as antibiotic resistance.

Preclinical studies have shown that over time (12-24 hours) the color of leftover products in the package might change from a white transparent tone to a more yellow-brown color. Change in color has not been associated with change in efficacy. To minimize risk of skin discoloration we will advise the subjects to rinse off the site in the morning.

Subjects with sensitivity to doxycycline might develop an allergic drug reaction, which could vary from local irritation to more severe systemic reaction. Subjects with sensitivity/allergy to

tetracycline will not be enrolled in the study.

In case of any abnormal reaction we will instruct the subjects to call the dermatology office and stop using NANODOX® until discussing symptoms with study team.

Risks to children or pets are not known and subjects will be instructed to keep the products out of reach from children and pets. Because this is an investigational medication/formulation some side effect may not yet be known. Any adverse reaction will be accounted.

Based on preliminary data, we do not anticipate any complications associated with the use of topical doxycycline.

Common skin reactions with taking oral doxycycline include:

- Redness
- Swelling
- Blistering rash

Common allergic reactions with taking oral doxycycline include:

- Hives
- Shortness of breath
- Swelling of the face, lip, tongue, or throat

Common systemic reactions with taking oral doxycycline include:

- Headache
- Dizziness
- Fever
- Chills
- Rash
- Nausea
- Vomiting
- Diarrhea
- Thrush
- Vaginitis

If a subject experiences an unexpected reaction to the investigational product, it should be recorded as an AE or SAE.

The study agent (NanoDOX™ Hydrogel) consists of doxycycline gel 1% w/w. The 1% w/w doxycycline formulation of NanoDOX™ Hydrogel contains: 1% w/w doxycycline monohydrate in carboxymethylcellulose (CMC), a hydrogel. CMC functions as the vehicle for the doxycycline active ingredient and assists in providing a moist wound environment. The primary function of doxycycline in NanoDOX™ Hydrogel is to promote wound healing by harnessing doxycycline's inhibition of matrix metalloproteinase (MMPs) and TNF- $\alpha$  converting enzyme (TACE). This property of doxycycline is hypothesized as the mechanism of action of NanoDOX™ Hydrogel for enhanced wound-healing.

Alchem will prepare, package and label the investigative material in easy-to-open 1.5 gram disposable packets. Each packet of doxycycline gel will have a two-part tear-off label. The gel should be refrigerated between applications.

#### Bench Testing

Systemic absorption of the doxycycline component in NanoDOX® Hydrogel through the skin was evaluated by Nanotherapeutics. Briefly, Franz diffusion cells were used to analyze the amount of doxycycline released out of a NanoDOX® Hydrogel or particle suspension across an exact area with respect to time. These conditions may be used to mimic an exposed wound and the resulting drug release out of the NanoDOX® Hydrogel into the body. Overall, less than 1% w/w of the 15 mg total doxycycline available in the donor chamber in the gel (11.18 $\mu$ g, or 0.08%) as well as the suspension (29.88 $\mu$ g, or 0.21% w/w) diffused across the membrane into the receptor chamber.

### Animal Testing

In a rat wound healing study, NanoDOX® Hydrogel was tested at doxycycline concentrations of 0.0% (placebo hydrogel), 0.3%, 1.0%, and 3.0% w/w as well as untreated control. The results of the study are:

- a) No significant differences between the histological scoring for all concentrations and the control; and,
- b) All concentrations were judged to be non-irritants versus the control.

Details relating to additional in vivo and in vitro nonclinical pharmacology and nonclinical toxicology studies of NanoDOX® Hydrogel can be found in the Investigator's Brochure.

